### 8.3 Exclusion criteria

Subjects must not enter the trial if any of the following exclusion criteria are fulfilled:

1. Concurrent enrolment in another clinical trial where the subject is receiving an IMP.
2. Previous randomisation in tralokinumab trials.
3. Subjects for whom administration of the meningococcal vaccine provided in this trial is contraindicated or medically inadvisable, according to local label of the vaccine.
4. Subjects for whom administration of the tetanus, diphtheria, and pertussis vaccine provided in this trial is contraindicated or medically inadvisable, according to local label of the vaccine.
5. Active dermatologic conditions that may confound the diagnosis of AD or would interfere with assessment of treatment, such as scabies, cutaneous lymphoma, or psoriasis.
6. Known active allergic or irritant contact dermatitis that is likely to interfere with the assessment of severity of AD.
7. Use of tanning beds or phototherapy (narrow band ultraviolet B [NBUVB], ultraviolet B [UVB], ultraviolet A1 [UVA1], psoralen + ultraviolet A [PUVA]), within 6 weeks prior to randomisation.
8. Treatment with the following medications within 4 weeks prior to randomisation:
  - Systemic immunosuppressive/immunomodulating drugs (e.g. methotrexate, cyclosporine, azathioprine, mycophenolate mofetil, Janus kinase inhibitors etc.).
  - Systemic corticosteroid use (excludes topical, inhaled, or intranasal delivery)
  - Three or more bleach baths during any week within the 4 weeks.
9. Treatment with the following medications within 2 weeks prior to randomisation
  - TCS.
  - TCI.
  - Topical PDE-4 inhibitor.

10. Receipt of any vaccine (except influenza virus vaccines) within 3 months prior to screening, any meningococcal vaccine within 1 year prior to screening, or any tetanus-, diphtheria-, or pertussis-containing vaccine within 5 years prior to screening, documented or subject-reported.
11. Receipt of any marketed (i.e. immunoglobulin, anti-IgE) or investigational biologic agent, including dupilumab:
  - Any cell-depleting agents including but not limited to rituximab: within 6 months prior to randomisation, or until lymphocyte count returns to normal, whichever is longer.
  - Other biologics: within 3 months or 5 half-lives, whichever is longer, prior to randomisation.
12. Receipt of any investigational non-biologic agent within 5 half-lives prior to randomisation.
13. Receipt of blood products within 4 weeks prior to screening.

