#### **9.2.2 Administration of vaccines**

At visit 9 (Week 12), subjects will each receive 1 dose of Tdap and meningococcal vaccines (refer to the schedule of trial procedures [Section 4]). The vaccines will be administered by trial staff on the same day the tralokinumab/placebo injections are administered; the vaccines will be given first, then tralokinumab/placebo will be given (see below).

The 2 vaccines will be given intramuscularly in the deltoid muscle of the upper arms, 1 vaccine in each arm. The injection site must be recorded in the source documents and recorded in the eCRF.

The subject will be kept under observation for 30 minutes following vaccination. After this observational period, the 2 tralokinumab/placebo injections will be given ([Panel 7](#)). Note that at Week 12, the tralokinumab/placebo injections will be given in the anterior thigh or abdomen.

Appropriate drugs, such as epinephrine, antihistamines, corticosteroids, etc., and medical equipment to treat acute anaphylactic reactions must be immediately available at trial sites, and trial personnel should be trained to recognise and respond to anaphylaxis according to local guidelines.

Syncope can occur in association with administration of the vaccines. Procedures should be in place to prevent falling injury and to restore cerebral perfusion following syncope.

For each vaccine, the IRT will assign the required kit number for each subject.

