**Panel 6: Prohibited medication**

Medication	Prohibited from	Prohibited to	Temporary discontinuation of IMP required
Topical medications used for treatment of AD, including: 
 
• TCS of any WHO class.
 
• TCI.
 
• PDE-4 inhibitors.
 
	Week -2 (2 weeks prior to randomisation)	Week 16 (end of treatment)	No
Use of UVA or UVB, psoralen + UVA (PUVA), other phototherapy, or tanning beds.	Week -6 (6 weeks prior to randomisation)	Week 16 (end of treatment)	No
Three or more bleach baths per week.	Week -4 (4 weeks prior to randomisation)	Week 16 (end of treatment)	No
Investigational agents other than tralokinumab.	3 months or 5 half-lives  prior to randomisation	Week 30 (safety follow-up)	Yes
Immunoglobulin.	3 months or 5 half-lives  prior to randomisation	Week 30 (safety follow-up)	Yes
Blood products.	4 weeks prior to screening	Week 30 (safety follow-up)	Yes
Systemic corticosteroids 	Week -4 (4 weeks prior to randomisation)	Week 30 (safety follow-up)	Yes
Systemic treatment for AD with an immunosuppressive or immunomodulating agent  .	Week -4 (4 weeks prior to randomisation)	Week 30 (safety follow-up)	Yes
Allergen immunotherapy.	Randomisation	Week 30 (safety follow-up)	Yes
Vaccination of any kind (except influenza virus vaccines).	3 months prior to screening	Week 30 (safety follow-up)	Yes

1) Whichever is longer. For cell-depleting agents, the use is disallowed within 6 months of randomisation.

2) Note: nasal and inhaled corticosteroids are allowed.

3) Examples include cyclosporine, mycophenolate mofetil, azathioprine, methotrexate, Janus kinase inhibitors, interferon-gamma, dupilumab, and other biologics.

AD, atopic dermatitis; IMP, investigational medicinal product; PDE-4, phosphodiesterase 4; TCI, topical calcineurin inhibitor; TCS, topical corticosteroid; UV, ultraviolet; WHO, World Health Organization.

In case any prohibited treatments are used during the trial, they must be recorded as concomitant medication.

Refer to Section 9.5 for principles for use of rescue treatment and re-initiation of IMP after discontinuation of prohibited systemic rescue treatment.

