## 10.2.2 Reasons for temporary discontinuation of IMP

IMP dosing may be temporarily suspended in the event of:

- Other intercurrent illnesses or major surgery.
- An infection that requires parenteral treatment with antibiotic, antifungal, antiviral, anti-parasitic, or anti-protozoal agents.
- Treatment with some of the prohibited medications given in [Panel 6](#) (medications requiring temporary discontinuation of IMP are highlighted in the column ‘Temporary discontinuation of IMP required’).

IMP dosing may resume after the medication leading to suspension of IMP is discontinued. Refer to [Section 9.5](#) for details regarding re-initiation of IMP after discontinuation of systemic rescue treatment.

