### 14.2 Trial analysis sets

All screened subjects will be accounted for in the CTR.

All subjects randomised to treatment are included in the FAS and will be analysed for efficacy up to Week 16. Exclusions from the FAS can be considered in special cases as described in

ICH E9, Section 5.2.1, Full Analysis Set. If it is decided to exclude a randomised subject from the FAS, a justification addressing ICH E9 will be given.

A per protocol analysis set will be defined by excluding subjects from the FAS for whom any of the following conditions apply:

- Receive no treatment with the IMP (vaccines).
- Provide no vaccine data at Week 16.
- Are known to have taken the wrong IMP throughout the treatment period.
- Do not fulfil the inclusion criteria no. 3, 6, 7, 8.
- Meet exclusion criterion related to receipt of other vaccines (that is, exclusion criterion no. 10).
- Initiate systemic rescue treatment prior to Week 10 and who are still treated with or exposed to systemic rescue treatment at Week 10 (that is, Week 10 [visit 8] occurs within 5 half-lives after the last dose of systemic rescue medication).
- Initiate systemic rescue treatment at Week 10 or later.
- Have missed more than 2 doses of tralokinumab/placebo before vaccine administration.
- Have missed any of the last 2 doses of tralokinumab/placebo before vaccine administration (that is, Weeks 8 and 10).

The per protocol analysis set will be used as primary analysis set for the vaccine antibody responses at Week 16 (primary endpoints; Panel 13). For the secondary endpoints (IGA 0/1 and EASI75 at Week 16), the FAS analysis will be considered primary.

A safety analysis set will be defined by excluding subjects from the FAS who received no treatment with IMP.

Based on the above-mentioned rules, the inclusion/exclusion of subjects or subject data from the trial analysis sets will be documented in the statistical analysis plan update before breaking the randomisation code.

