The safety analysis set comprises all subjects randomised to treatment who were exposed to IMP. The protocol further specifies to exclude subjects from the safety analysis set for whom no post-baseline safety data are available. However, since all subjects receive the first dose of IMP in connection with the Week 0 visit and are subsequently monitored for immediate drug reactions, all exposed subjects are considered to have post-baseline safety data available and no such further exclusions will be made.

In addition to the analysis sets defined in the protocol, a safety follow-up analysis set will be used as the basis for evaluation of adverse events during the safety follow-up period. It comprises all subjects for whom date of last contact is after the date of exposure end, where exposure end is defined as the Week 16 visit for subjects completing the treatment period, and otherwise the date of permanent discontinuation of IMP (tralokinumab/placebo) for subjects not completing the treatment period. See also Section 6.9.2 for further details.

For analysis of efficacy, subjects will be included 'as randomised'.

For analysis of safety, if a subject is mistakenly given an IMP other than that to which they were randomised, they will be analysed 'as treated', thus included in the group according to the therapy actually received by the subject. The below rules will be applied.

Subjects who received at least one dose of tralokinumab will be analysed in the tralokinumab treatment group. Although this may dilute the AE rate in the tralokinumab treatment group slightly by including in the denominator subjects who only received one dose of active treatment, it will ensure that no significant drug reactions to tralokinumab will erroneously be assigned to placebo.

The definition of the per protocol analysis set as described in the protocol has been updated to accept negligible deviations in baseline disease severity related to the EASI status. Thus, the criteria from inclusion criterion 7 have been modified to require an EASI score of ≥ 12 at screening OR ≥ 16 at baseline instead of requiring both criteria to be met. The rationale for this change is that marginal deviations in baseline disease severity is not considered to affect the vaccine response.

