The criteria related to systemic rescue medication in the definition of the per protocol analysis set have been updated relative to the protocol text to include, not only those for the AD indication but all systemic immunosuppressive treatments irrespectively of indication. The referred criteria for excluding patients consequently become:

- Initiated systemic immunosuppressive treatment prior to Week 10 and who are still treated with or exposed to the given treatment at Week 10 (that is, Week 10 [visit 8] occurs within 5 half-lives after the last dose of the given systemic immunosuppressive medication).
- Initiated systemic immunosuppressive treatment at any time point from Week 10 to Week 16.

The rationale for excluding these subjects is to ensure that subjects were not immunosuppressed by these treatments when the vaccinations were administered, as this might impact the response to the vaccination, and thereby the primary endpoints. This is independent of the indication for the immunosuppressive treatments and should therefore include all subjects treated with systemic immunosuppressants, irrespectively of the indication.

In addition to the criteria specified in the protocol, subjects with Week 16 visit occurring ≥ 56 days after the Week 12 visit, are not included in per protocol analysis set due to a too long interval between administration of the vaccine and measurement of the vaccine response, since this would induce a risk of a perished vaccine response.

Systemic immunosuppressive treatment definition

ATC2 code H02 or L04 will be used to identify administered systemic immunosuppressive treatments. [Table 1](#) below presents the medications that as minimum will be identified in the trial (as being systemic immunosuppressive) along with the half-lives applied to evaluate the PP exclusion criteria.

Medications administered in the screening period will be included in the search to ensure that all administered medications that could potentially be immunosuppressive at time of vaccination will be covered. Different routes of administration can be used for the medications, which will result in different half-lives.

Table 1: Systemic immunosuppressive treatments and applied halflives

ATC 4	ATC 4 TERM	Standardized Medication Name	Route of Administration	Halflife		
				Hours	Weeks	5 x t _{1/2} ¹
H02AB	GLUCOCORTICOIDS	DEXAMETHASONE	ORAL	7.2	0.0	0.2

H02AB	GLUCOCORTICOIDS	DEXAMETHASONE SODIUM PHOSPHATE	INTRAVENOUS	24	0.1	0.7

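### The per-protocol set that decides non-inferiority has no rule for prohibited vaccines, immunoglobulin or blood products received during the trial, so such subjects leave it only incidentally

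*Protocol*

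**What the plan says.** Protocol 14.2 and 14.3.5 make the per-protocol set primary for both Week 16 antibody endpoints. The full analysis set (FAS) is analysed as well, on observed data.

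On other vaccines, the per-protocol list removes only subjects who "Meet exclusion criterion related to receipt of other vaccines (that is, exclusion criterion no. 10". That criterion (Protocol 8.3) opens "Receipt of any vaccine (except influenza virus vaccines) within 3 months prior to screening, any meningococcal vaccine within 1 year prior to screening" and goes on to tetanus-, diphtheria- or pertussis-containing vaccines within 5 years before screening. Criterion 11, which names immunoglobulin, and criterion 13 ("Receipt of blood products within 4 weeks prior to screening") are not on the per-protocol list.

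Panel 6 (Protocol 9.7) prohibits "Vaccination of any kind (except influenza virus vaccines"), immunoglobulin and blood products up to Week 30. It marks each as requiring temporary discontinuation of IMP. Under Protocol 10.2.2, "IMP dosing may resume after the medication leading to suspension of IMP is discontinued".

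SAP section 5 changes three things in the per-protocol definition: the EASI criterion, systemic immunosuppressants (ATC H02 or L04), and a Week 12 to Week 16 interval of 56 days or more. It removes users of immunosuppressants, whatever the indication, because they may be immunosuppressed when vaccinated, "as this might impact the response to the vaccination, and thereby the primary endpoints". SAP Table 1 lists no vaccine, immunoglobulin or blood product. SAP 6.9.6 summarises and lists major deviations but excludes nobody.

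**The concern.** Both endpoints are built from IgG at Week 12 and Week 16, and a product from outside the trial can bear on either value. A tetanus booster before Week 12 that lifts IgG above 1.0 IU/mL moves the subject from the 3-fold rule to the fixed 2.5 IU/mL rule. A meningococcal vaccine before Week 12 raises the level that must triple. After Week 12, a further booster or immunoglobulin may add IgG that the trial vaccine did not produce.

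The plan already treats outside vaccination as relevant, since criterion 10 is a per-protocol exclusion. Yet a tetanus vaccine 4 years before screening removes a subject, while one given at Week 13 does not. The reason the SAP gives for removing immunosuppressant users applies equally here. The FAS analysis keeps the same subjects, so comparing the two sets would not show the effect.

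**Working it through.** **1. Which rules can remove a subject after such a breach**

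- *Screening (2 to 6 weeks).* No dose is due, so the missed-dose rules cannot act. For immunoglobulin, the criterion 11 window runs to randomisation and eligibility is checked again on Day 0 (Protocol 7.1), so the subject should not be randomised. One randomised in error is not removed, because criterion 11 is not on the list. The criterion 10 and 13 windows have already closed at screening.
- *Weeks 0 to 12.* A subject leaves for missing the Week 8 or Week 10 dose, or more than 2 doses before vaccination. The SAP notes that "since all subjects receive the first dose of IMP in connection with the Week 0 visit", so the remaining earlier doses are those at Weeks 2, 4 and 6. A breach that costs none, one or two of these three leaves the subject in. A subject who never receives the trial vaccines is removed.
- *Weeks 12 to 16.* At Week 12 "the vaccines will be given first, then tralokinumab/placebo will be given", so a dose missed at Week 12 or Week 14 is not a dose missed before vaccination. Only missing Week 16 vaccine data or an interval of 56 days or more can remove the subject.

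Every one of these routes acts for a reason other than receipt of the product.

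**2. The plan's own figures** (Protocol 14.1: 80% in both arms, margin -25 points, one-sided 2.5%, 160 per protocol, i.e. 80 per arm; 200 in the FAS)

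Tetanus power = Φ(0.25 / √(2 × 0.8 × 0.2 / 80) - 1.96) = Φ(3.953 - 1.960) = 97.7%, against 98% stated.

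All four hypotheses, with 100 per arm for the secondary endpoints: 0.977² × 0.948 (IGA 30% v 10%) × 0.981 (EASI75 40% v 15%) = 88.8%, against about 89% stated.

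**3. Distance from the margin at the planned rates**

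Wald lower limit at 64/80 in each arm: 0 - 1.96 × √(2 × 0.8 × 0.2 / 80) = -12.4 points. With placebo held at 64/80, tralokinumab at 55/80 gives -24.7 and at 54/80 gives -26.0. Ten responders would have to be lost in one arm before non-inferiority failed.

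**4. Illustration at the margin**

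The documents give no breach rate, so 1 or 2 affected subjects per arm is an assumption. True rates are 80% on placebo and 55% on tralokinumab, with 80 per arm. If c subjects in each arm respond regardless of treatment, or have their response masked regardless of treatment, the difference becomes -25 × (1 - c/80). For one responder in tralokinumab only it is (0.55 × 79 + 1)/80 - 0.80 = -24.4; in placebo only it is 0.55 - (0.80 × 79 + 1)/80 = -25.25.

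| Affected subjects | Difference (points) | False non-inferiority, normal approximation | Exact enumeration of the Wald rule |
|---|---|---|---|
| None | -25.0 | 2.5% | 2.4% |
| 1 per arm, respond | -24.7 | 2.8% | 2.6% |
| 2 per arm, respond | -24.4 | 3.1% | 2.9% |
| 1 per arm, masked | -24.7 | 2.8% | 2.5% |
| 2 per arm, masked | -24.4 | 3.0% | 2.6% |
| 1 responder, tralokinumab only | -24.4 | 3.0% | 2.85% |
| 1 responder, placebo only | -25.25 | 2.3% | 2.2% |

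The normal column is Φ((d + 0.25)/SE - 1.96). All figures ignore the IGA stratification.

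**5. Cost of excluding them**

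If 2 of 160 are lost (79 per arm), tetanus power is 97.5% and joint power 88.5%. If 4 are lost (78 per arm), they are 97.4% and 88.3%.

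**The case against.** The best case against acting is size. The products are prohibited, the number of breaches is probably small, the planned result lies ten responders from failing, and even at the margin the exact error moves by half a point or less. That stands, and it sets the priority low.

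The per-protocol list is also selective by design, citing only four inclusion criteria and one exclusion criterion, and each further post-randomisation exclusion carries some selection risk. That is fair, but the same risk attaches to the existing rescue, missed-dose and interval rules. A by-arm listing or a sensitivity analysis would reveal the problem while leaving the deciding analysis unchanged.

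The move to the 2.5 IU/mL rule is intended: Protocol 12 says that the tetanus definition allows for high pre-vaccination levels. This lessens the effect of an early booster on that endpoint. It does nothing for the meningococcal endpoint or for a product given after Week 12. The documents also do not say how much specific IgG immunoglobulin or a blood product would add, so that part of the mechanism is an assumption without a size.

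A reader might infer that the missed-dose rules are the only way out, or that screening and Weeks 12 to 16 are wholly unguarded. The documents do not support this. Absent trial vaccination, missing Week 16 data and the 56-day rule also remove subjects, and criterion 11 with the Day 0 check guards against immunoglobulin during screening.

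**Conclusion.** The gap is in the text of both documents. The set that decides non-inferiority contains no rule on receipt of these products during the trial, and the routes that might remove such a subject are incidental. Keeping them is at odds with the plan's use of criterion 10 and with the SAP's reason for removing immunosuppressant users.

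The likely effect is small. At the planned rates a few subjects would not change the conclusion; the point matters only if the result falls near -25. The illustrated rise from 2.4% to 2.6% or 2.9% rests on an assumed 1 or 2 responders per arm and a true difference exactly at the margin.

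A reader might infer that the gap favours tralokinumab or undermines the trial's conclusion. The documents do not support either inference: they give no count, and the direction depends on which arm the subjects are in and on whether their response is created or masked.

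**What to change.** In SAP section 5, before unblinding, also exclude from the per-protocol set subjects who, up to the Week 16 sample, receive:

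- (a) a non-trial tetanus-, diphtheria-, pertussis- or meningococcal-containing vaccine after screening. These are the groups criterion 10 names. They bear on the measured antigens or, for diphtheria toxoid, on the carrier of the meningococcal vaccine (Panel 5); pertussis-containing vaccines follow criterion 10's grouping. List other prohibited vaccines by arm.
- (b) immunoglobulin or a blood product, counted from the start of the criterion 11 or criterion 13 window respectively, so that breaches before screening are covered too.

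Identify these subjects under blind from recorded concomitant medication (Protocol 9.6), within the blinded review already planned (Protocol 14.3.10). Report counts per arm and show the planned FAS result beside the per-protocol result.

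The cost is one more criterion. The record runs from 3 months before screening to Week 30, so little or no new data collection is needed; the one exception would be a criterion 11 window of 5 half-lives that reaches back further, and the documents give no half-life for immunoglobulin. The downsides are a further post-randomisation exclusion, which is why counts by arm are needed, and the small loss of power shown above.

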## 14.3 Statistical analysis

### 14.3.1 Disposition of subjects

For all randomised subjects the reasons for permanent discontinuation of IMP and for leaving the trial will be presented by treatment group.

### 14.3.2 Demographics and other baseline characteristics

Descriptive statistics of demographics and other baseline characteristics will be presented for all randomised subjects and the per protocol analysis set. The presentations will be overall and by treatment group. Presentations of age, sex, ethnicity, and race will also be given by baseline disease severity (IGA 3 or 4).

Demographics include age, sex, race, and ethnicity. Other baseline characteristics include vital signs (including height, weight, body mass index), duration of AD, concurrent diagnoses (from medical history and indications for concomitant medication), concomitant medication, and previous AD treatments.

